7.3.9. DLCO

Endpoint: Pulmonary function tests will be performed at Screening, Week 24, and Week 48; only DLCO will be collected at the Week 24 and 48 visits. Data for DLCO will be collected on the Pulmonary Function Tests CRF pages. Lower DLCO values indicate worse disease activity. DLCO will be calculated according to the Global Lung Function Initiative (GLI) all-age reference values and corrected for hemoglobin. The hemoglobin used for adjustment should be done within two weeks of the PFT test and will be recorded on the CRF page. If a hemoglobin measure is not available, the unadjusted value will not be used. The % predicted DLCO is computed as the measured DLCO divided by the computed predicted value and multiplied by 100%. Change from baseline in the % predicted DLCO will be calculated.

Analysis: Analyses analogous to those specified in Section 7.3.5, *Quality of Life: SF-36*, will be performed for DLCO.

7.3.10. Oxygen Saturation

Endpoint: Oxygen saturation will be recorded at Screening, Day 0, Weeks 4, 12, 24, 36, and 48, and will be collected on the Oxygen Saturation CRF page. If possible, oxygen saturation

will be measured on room air; if oxygen saturation is <90% on room air, then the flow rate required to maintain saturation $\geq 90\%$ will be recorded. If a subject is unable to have oxygen saturation measured on room air and supplemental oxygen is required, then the flow rate required to maintain saturation $\geq 90\%$ will be recorded.

Additionally, oxygen saturation is recorded at Screening and Weeks 4, 12, 24, 36, and 48 on the 6-Minute Walk Test CRF page, using the “pre walk” values. Oxygen saturation values and whether the value was recorded on room air or supplemental oxygen will be recorded. If oxygen saturation is measured on supplemental oxygen, then the flow rate used will be recorded as well.

Analysis: Oxygen saturation on room air and flow rate required to maintain saturation $\geq 90\%$ will be summarized by treatment group and overall by study visit.

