2.2 Secondary Objectives

Secondary Efficacy Objectives:

- To compare patients treated with rituximab to those on placebo for change in exercise capacity, as determined by 6MWD, at time points other than 24 weeks.
- To compare patients treated with rituximab to those on placebo for change in PVR as assessed by right heart catheterization.
- To compare patients treated with rituximab to those on placebo for time to clinical worsening, defined as first occurrence of:
 - a. death,
 - b. hospitalization for SSc-PAH,
 - c. lung transplantation,
 - d. atrial septostomy,
 - e. addition of other PAH therapeutic agents, or
 - f. worsening of 6MWD by > 20% and a decrease in functional class.
- To compare patients treated with rituximab to those on placebo who changed or added other PAH therapeutic agents.

- To compare patients treated with rituximab to those on placebo for change in quality of life as determined by the short form 36 (SF-36) and the disability index of the Scleroderma Health Assessment Questionnaire (SHAQ).
- To compare patients treated with rituximab to those on placebo for change in number of new digital ulcers.
- To compare patients treated with rituximab to those on placebo for change in severity of Raynaud phenomenon as measured by the VAS scale of the SHAQ.
- To compare patients treated with rituximab to those on placebo for change in DLCO and room air oxygen saturation at rest .

A secondary objective of this study is to determine whether the effects on clinical disease progression are paralleled by changes in selected biomarkers.

Secondary Safety Objectives:

- To assess the safety and tolerability of rituximab for the treatment of SSc-PAH in patients receiving stable background medical treatment with prostanoid, endothelin receptor antagonist, PDE-5 inhibitor therapy, and/or guanylate cyclase stimulators.

Mechanistic Study Objectives:

- CD19 Studies
 - To determine whether the extent and/or duration of CD19+ B cell depletion correlates with treatment response as measured by PVR (right heart catheterization), exercise capacity (6MWD), and quality of life (SF-36 and SHAQ).
 - To monitor and correlate the reconstitution patterns of B cell subpopulations with treatment response.

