3.2.2 Secondary Efficacy Endpoints

Secondary efficacy endpoints include the following clinical endpoints:

1. Change in PVR measured by right heart catheterization from baseline to 24 weeks after treatment initiation.
2. Exercise capacity, as determined by 6MWD, assessed longitudinally over the 48 weeks following treatment initiation.
3. Assessment of time to clinical worsening, censored at 48 weeks, defined as first occurrence of:
 - a. death,
 - b. hospitalization for SSc-PAH,
 - c. lung transplantation,
 - d. atrial septostomy,
 - e. addition of other PAH therapeutic agents, or
 - f. worsening of 6MWD by > 20% and a decrease in functional class.
4. Percentage of subjects who changed or added PAH therapeutic agents at 24 and 48 weeks.
5. Change in quality of life as determined by the SF-36 and disability index of the SHAQ from baseline to 24 and 48 weeks after treatment initiation.
6. Number of new digital ulcers assessed longitudinally over both the 24 and 48 weeks following treatment initiation.
7. Severity of Raynaud phenomenon, as measured by the VAS scale of the SHAQ, assessed longitudinally over both the 24 and 48 weeks following treatment initiation.
8. DLCO and oxygen saturation at rest on room air assessed longitudinally over both the 24 and 48 weeks following treatment initiation.
9. Change in PVR from baseline to 24 weeks after treatment initiation as a percentage of the baseline value.

Secondary efficacy endpoints also include the following mechanistic endpoints:

1. CD19 Studies
 - a. CD19+ B cells (absolute number and percentage of gated lymphocytes) at time of B cell depletion and longitudinally over the 48 weeks following treatment initiation, where B cell depletion is defined as < 5 CD19+ cells/ μ L.
 - b. Time to repopulation of CD19+ B cells, defined as the time point at which B cells recover to within 10% of baseline levels; if a baseline value is not available then recovery is defined as a B cell level of at least 90% of the lower limit of normal.

- c. Reconstitution pattern of B cell subpopulations assessed longitudinally over the 48 weeks following treatment initiation.
2. Level of anti-U1 RNP, anti-B23, anti-cardiolipin, anti-CENP-B, RF autoantibodies, and immunoglobulins, including IgG subclasses, measured by ELISA and assessed longitudinally over the 48 weeks following treatment initiation.

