Longitudinal changes in the six-minute walk distance at week 48 will be assessed using a similar model as the primary endpoint, but including all data through 48 weeks. This model will address any subject who had their 6MWD affected by new or changed PAH therapeutic agents after the 24 week time point. Additionally, the analysis will be conducted on the ITT population will additionally add limited by any musculoskeletal disease (yes/no) as a covariate. Additional models may be developed to assess the effect of other covariates.

Longitudinal change in the oxygen saturation will be compared across the two arms using generalized estimating equations. An ordinal response variable will be used to account for the subjects that cannot perform the room air assessment. Initially the model will be used to describe changes between baseline and 24 weeks and baseline and 48 weeks including only treatment, baseline levels of oxygen saturation, and an indicator if the measurement was affected by changed or new PAH therapeutic agents, with added models developed to assess the effect of other covariates. However, if all subjects can perform the room air assessment, the data will be analyzed as a continuous model, following the method described above for the six-minute walk distance.

Longitudinal change in number of new digital ulcers will be compared across the two arms using Poisson marginal models for longitudinal data. Initially the models will be used to describe changes between baseline and 24 weeks and baseline and 48 weeks including only treatment, baseline levels of the outcome of interest, and an indicator if the measurement was affected by changed or new PAH therapeutic agents , with added models developed to assess the effect of other covariates.

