1. PROTOCOL SYNOPSIS

Title of the Protocol: A Randomized, Double-blind, Placebo-Controlled, Phase II Multicenter Trial of a Monoclonal Antibody to CD20 (Rituximab) for the Treatment of Systemic Sclerosis-Associated Pulmonary Arterial Hypertension (SSc-PAH)
ACE Protocol Number: ASC01
Protocol Chair(s): [name]; [name]
IND Holder: DAIT/NIAID/NIH
Primary Objective: The primary objective of this study is to compare patients with SSc-PAH treated with rituximab to those on placebo for change in exercise capacity, as determined by six minute walk distance (6MWD).
Secondary Efficacy Objectives: 
• To compare patients treated with rituximab to those on placebo for change in exercise capacity, as determined by 6MWD, at time points other than 24 weeks.• To compare patients treated with rituximab to those on placebo for change in PVR as assessed by right heart catheterization.• To compare patients treated with rituximab to those on placebo for time to clinical worsening, defined as first occurrence of:
a. death,b. hospitalization for SSc-PAH,c. lung transplantation,d. atrial septostomy,e. addition of other PAH therapeutic agents, orf. worsening of 6MWD by > 20% and a decrease in functional class.• To compare patients treated with rituximab to those on placebo who changed or added other PAH therapeutic agents.• To compare patients treated with rituximab to those on placebo for change in quality of life as determined by the short form 36 (SF-36) and the disability index of the Scleroderma Health Assessment Questionnaire (SHAQ).• To compare patients treated with rituximab to those on placebo for change in number of new digital ulcers.• To compare patients treated with rituximab to those on placebo for change in severity of Raynaud phenomenon as measured by the VAS scale of the SHAQ.• To compare patients treated with rituximab to those on placebo for change in DLCO and room air oxygen saturation at rest. 
A secondary objective of this study is to determine whether the effects on clinical disease progression are paralleled by changes in selected biomarkers.
 Secondary Safety Objectives: 
• To assess the safety and tolerability of rituximab for the treatment of SSc-PAH in patients receiving stable background medical treatment with prostanoid, endothelin receptor antagonist, PDE-5 inhibitor therapy, and/or guanylate cyclase stimulators.

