3. GENERAL ANALYSIS AND REPORTING CONVENTIONS

The following analyses and reporting conventions will be used:

- Categorical variables will be summarized using counts (n) and percentages (%) and will be presented in the form “n (%)” Percentages will be rounded to one decimal place.
- Numeric variables will be summarized using n, mean, standard deviation (SD), median, minimum (min), maximum (max). The min/max will be reported at the same level of significance as original data. The mean and median will be reported at one more significant digit than the precision of the data, and SD will be reported at two more significant digits than the precision of the data.
- The median will be reported as the average of the two middle numbers if the dataset contains an even number of observations.
- Test statistics including *t* and *z* test statistics will be reported to two decimal places.
- *P*-values will be reported to three decimal places if greater than or equal to 0.001. If less than 0.001, the value will be reported as “<0.001.” A *p*-value can be reported as “1.000” only if it is exactly 1.000 without rounding. A *p*-value can be reported as “0.000” only if it is exactly 0.000 without rounding.

If departures from these general conventions are present in the specific evaluations section of this SAP, then those conventions will take precedence over these general conventions.

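### SAP 7.3.10 drops the protocol's between-arm ordinal model for room-air oxygen saturation without declaring it, so this secondary endpoint has no estimated treatment contrast

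*SAP*

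**What the plan says.** Protocol 2.2 sets the objective: "To compare patients treated with rituximab to those on placebo for change in DLCO and room air oxygen saturation at rest". Protocol 3.2.2 makes it secondary endpoint 8: "DLCO and oxygen saturation at rest on room air assessed longitudinally over both the 24 and 48 weeks following treatment initiation".

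Protocol 8.3.2.2 gives the analysis: "Longitudinal change in the oxygen saturation will be compared across the two arms using generalized estimating equations". It explains the response type: "An ordinal response variable will be used to account for the subjects that cannot perform the room air assessment". The initial model contains treatment, baseline saturation and an indicator for changed or new PAH agents, and covers baseline to Week 24 and baseline to Week 48. There is one fallback: "if all subjects can perform the room air assessment, the data will be analyzed as a continuous model".

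The SAP synopsis repeats the objective ("for change in DLCO and room air oxygen saturation at rest") and endpoint 8. The whole analysis paragraph of SAP 7.3.10 says that "Oxygen saturation on room air and flow rate required to maintain saturation" at 90% or above will be summarized by treatment group and overall at each visit.

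**The concern.** The SAP keeps a between-arm objective but plans nothing that estimates a between-arm difference. The dropped method was also the protocol's answer to a foreseen problem: some subjects will have no room-air value. Inclusion criterion 8 admits subjects who reach 90% with oxygen, and protocol 6.5 leaves the room-air test to the physician's discretion and rules it out where safety would suffer.

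At stake are the treatment contrast for one secondary endpoint and the meaning of the room-air means shown in its place. Those means describe only the subjects who could be tested at that visit, and that group can differ between arms and change between visits.

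**Working it through.** No figure in the plan needs reproducing. The check is a comparison of texts, followed by an illustration on assumed inputs.

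**1. Protocol against SAP**

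| Item | Protocol 8.3.2.2 | SAP 7.3.10 |
|---|---|---|
| Between-arm comparison | GEE | None |
| Subject with no room-air value | Kept, through an ordinal response | Flow rate recorded; no room-air value |
| Covariates | Treatment, baseline saturation, PAH-change indicator | None |
| Change from baseline | Baseline to Weeks 24 and 48 | Not defined |

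**2. Is this the SAP's general style?** No. SAP 7.3.1 to 7.3.9 each specify a between-arm comparison (mixed model, log-rank test or Poisson GEE) or refer to a section that does. SAP 7.3 foresees p-values and 95% intervals for secondary analyses, but 7.3.10 defines no contrast to which they could apply.

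**3. Is the change declared?** Protocol 8.5.6 says that major changes will be noted in the SAP. The numbered items in SAP Section 11 concern 7.2.2, 7.3.3 and 7.3.4. They go down to using visit week in place of visit day. Section 7.3.10 is not among them.

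**4. Who is missing from the room-air mean?** SAP Section 3 includes the mean among its numeric summaries, and SAP 7.3 rules out imputation. A subject not tested on room air therefore contributes no value. A subject tested on room air and found below 90% does have a value and stays in the mean; the flow rate is recorded in addition.

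**5. How much could this matter?** The documents give neither a saturation distribution nor a count of unmeasured subjects, so every input here is an assumption. Take room-air saturation as normal with mean μ of 93% in the worse arm and 95% in the better arm (true difference 2.0 points) and SD σ. Let a cut-off c stand in for non-measurement. With a = (c − μ)/σ:

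- share unmeasured = Φ(a)
- mean of those measured = μ + σ·φ(a)/(1 − Φ(a))

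Example with σ = 5 and c = 88:

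- Worse arm: a = −1.0, Φ = 0.159, mean = 93 + 5 × 0.2420/0.8413 = 94.438.
- Better arm: a = −1.4, Φ = 0.081, mean = 95 + 5 × 0.1497/0.9192 = 95.814.
- Observed difference: 95.814 − 94.438 = 1.38.

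| σ | c | Unmeasured, worse arm | Unmeasured, better arm | Observed difference |
|---|---|---|---|---|
| 3 | 86 | 1.0% | 0.1% | 1.93 |
| 4 | 86 | 4.0% | 1.2% | 1.77 |
| 4 | 88 | 10.6% | 4.0% | 1.54 |
| 5 | 88 | 15.9% | 8.1% | 1.38 |

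The shrinkage runs from (2.0 − 1.93)/2.0 = 3.5% to (2.0 − 1.38)/2.0 = 31%. With 30 subjects per arm, 15.9% is 0.159 × 30 = 4.8 subjects. Neither cut-off is a rule in the documents.

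**The case against.** The case on the other side is substantial.

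- **Little inference is lost.** Both documents treat every secondary analysis as exploratory, with descriptive p-values and intervals. This stands. It limits the consequence but does not explain why one planned comparison disappears while the others stay.
- **The objective is not abandoned.** A reader might infer that the trial can no longer address it at all. The documents do not support that: the objective pairs saturation with DLCO, DLCO keeps its model (SAP 7.3.9, through 7.3.5), and by-arm saturation summaries still allow a descriptive look.
- **Unmeasured subjects are not lost.** They appear in the flow-rate summary. This stands. However, that summary also holds flow rates for subjects who were measured and fell below 90%, and nothing combines the two summaries into one treatment comparison.
- **There may be no exclusion.** If every subject can be tested on room air, no one is left out. The protocol allows for that case, but its answer is a continuous between-arm model, which the SAP also omits.
- **The ordinal model is under-specified.** The protocol never defines the categories, and with about 60 subjects a sparse worst category could make the fit unstable. This stands and shapes the fix.

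**Conclusion.** The point holds as an undeclared departure from the protocol on one exploratory secondary endpoint. Followed as written, the SAP gives no estimated between-arm contrast for room-air saturation, and its room-air means leave out subjects who cannot be tested on room air.

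The effect on those means is likely, not established. That the unmeasured subjects are the sicker ones is an inference from the safety rule; no document says so. If it is right, the means are likely too high and a real difference is likely understated. Under the stated assumptions a true 2.0-point difference appears as about 1.9 when very few are unmeasured and about 1.4 when about 16% of the worse arm is. The true share is not given.

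A reader might take 90% as the point below which values are missing and arrive at a larger loss. SAP 7.3.10 does not support this, because a room-air reading below 90% is a recorded value and remains in the mean. The primary result is unaffected.

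**What to change.** In SAP 7.3.10, restore the protocol's ordinal GEE with treatment, baseline saturation and the PAH-change indicator. Specify:

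- not measurable on room air as the worst category;
- every subject with a measured room-air value classified by that value. Merging all subjects who need oxygen into the worst category would discard measured data;
- a small number of categories, fixed in advance;
- between-arm contrasts with 95% intervals at Weeks 24 and 48;
- the protocol's continuous model if all subjects are measurable.

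Keep the planned summaries.

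The cost is one extra exploratory model on data already collected, plus the work of defining the categories. The model may be unstable with about 60 subjects if few fall in the worst category. If it proves infeasible, list its removal in SAP Section 11 and give the reason.

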7.4. Examination of Subgroups

Secondary analyses of the primary and secondary objectives may be conducted for the following subgroups, including, but not limited to:

- Race
- Ethnicity
- Gender
- Baseline PVR
- Baseline 6MWD
- NYHA Functional Class
- Duration of SSc-PAH disease

Additionally, exploratory analyses of responder subgroups and subgroups defined through the mechanistic and immunological studies may also be conducted.

8. SAFETY EVALUATION

8.1. Overview of Safety Analysis Methods

All safety analyses will be carried out using the safety sample defined in Section 4 unless otherwise noted. Missing safety information will not be imputed. These analyses will not be stratified by site.

Listings will be prepared for applicable safety measurements. All listings will be sorted in order of treatment, subject identifier (ID), and time of assessment (e.g., visit, time, and/or event).}

8.2. Adverse Events

All AEs will be classified by system organ class (SOC) and preferred term, according to a standardized thesaurus (Medical Dictionary for Regulatory Activities [MedDRA] version 13.1). The severity of AEs will be classified using the National Cancer Institute's (NCI's) Common Toxicity Criteria for Adverse Events (CTCAE) version. Each AE is entered on the electronic case report form (eCRF) once at the highest severity. As such, no additional data manipulation is needed to identify events.

Adverse events NCI-CTCAE grade 2 and above will be collected from the time the subject signs the informed consent until he/she initiates study intervention or until he/she is determined to be ineligible to receive study intervention, if the investigator determines that the adverse event is related to a study-mandated procedure, treatment, or change in treatment.

For all participants, adverse events NCI-CTCAE grade 2 and above will be collected from the time of initiation of study intervention (i.e., the administration of the first dose of study drug/study drug) until he/she completes study participation or until 30 days after he/she prematurely withdraws (without withdrawing consent) or is withdrawn from the study. During the quarterly monitoring period of the study, only NCI-CTCAE grade 3 and higher infections are collected on the adverse events CRF page. Grade 3 and higher infections that occur during the quarterly monitoring period will be listed separately and will not be included in data tabulations, unless otherwise specified.

Treatment-emergent AEs will be identified as those with an onset date on or after the first dose of study medication. If the start of the AE in relation to the start of study medication cannot be established (e.g., the start date for the AE is missing), then the AE will be considered treatment-emergent. All data tabulations will be of only treatment-emergent events unless otherwise specified; non-treatment-emergent AEs will be listed.

An overall summary table will be developed to report the number of events and the number and percentage of subjects having at least one event in the following categories:

- AEs
- AEs requiring 24-hour reporting to the sponsor
- AEs indicated as serious
- AEs that lead to study drug discontinuation
- AEs with an outcome of death
- AEs by relationship to a study drug
- AEs reported by maximum severity
- All NCI-CTCAE Grade 3-5 AEs, which are defined as possibly, probably, or definitely related to rituximab
- All NCI-CTCAE Grade 3-5 adverse events

- All infection related AEs

In addition, AEs classified by MedDRA SOC and preferred term will be summarized for each treatment group and overall for each of the following:

- All AEs
- AEs by maximum severity
- AEs by relationship to study drug: relationship to study treatment will be categorized as either treatment related (possibly, probably, or definitely related to study medication) or unrelated
- All infection related AEs

Summary tables will present the total number of events as well as the number and percentage of subjects experiencing the events. If a subject experiences the same AE on multiple occasions, the event will be counted once for each occurrence when reporting the number of AEs. When reporting the number of subjects experiencing the events, a subject will only be counted once if they experience an event within the particular SOC or preferred term. Percentages will be based on the number of subjects in the safety population.

AEs classified by MedDRA system organ class and preferred term will be summarized for each treatment group and overall, and incidence rates for AEs classified by MedDRA SOC and preferred term will be provided for each treatment group and overall. The incidence rate for a SOC or preferred term will be defined as the number of AEs divided by the person-time of exposure aggregated in each treatment group, and an analysis based on a Poisson regression model will be conducted to compare the rate of each type of event in the treatment groups. The proportion of subjects in each study arm experiencing each type of AE will be compared using a Fisher's Exact test.

Separate data listings will be provided for the following subsets:

- Treatment-related AEs
- AEs leading to study drug discontinuation
- Grade 3-5 AEs which are defined as possibly, probably, or definitely related to rituximab
- All Grade 3-5 AEs
- Infections
- Grade 3 and higher infections that occurred during the quarterly monitoring period
- AEs occurring from informed consent and prior to treatment initiation

